4.5. Pharmacokinetic Analyses

4.5.1. Study Variables

4.5.1.1. Concentration Data

Urinary concentrations of ALN-18328 (siRNA) and 4-dimethylaminobutyric acid, as well as plasma concentrations of ALN-18328, DLin-MC3-DMA and PEG₂₀₀₀-C-DMG will be obtained. Concentration values that are below the limit of quantification (LLOQ or BLQ) will be set to zero for analysis.

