- n. Weight from previous visit should be used for calculating dose. Weight must be collected pre-dose.
- o. Vital signs to include: blood pressure, pulse rate, temperature, and respiratory rate. Parameters are to be measured in the supine position using an automated instrument after the patient has rested comfortably for 10 minutes. Vital signs must be collected pre-dose. On Day 0, vital signs will also be collected post-dose.
- p. All ECGs are to be obtained in triplicate.
- q. Blood samples for anti-drug antibody testing will be collected prior to study drug dosing.
- r. A pregnancy test (urine- or serum-based) will be performed on all females of child-bearing potential.
- s. The baseline ophthalmology examination may be performed any time after the patient is deemed eligible for participation in the study through Day 21. The 9-month ophthalmology examination will be performed between Days 231(±3) and 272 at a CAS.
- t. Plasma PK samples will be collected as follows: Day 0: pre-dose (within 1 hour of planned study drug dosing) and at the end of infusion (+5 minutes). Day 21 and Day 252: pre-dose (within 1 hour of planned study drug dosing) and 30 minutes after the end of the infusion (+15 minutes). Day 126: pre-dose (within 1 hour of planned study drug dosing) and at the end of infusion (+5 minutes).
- u. Urine PK samples will be collected pre-dose (within 1 hour of planned study drug dosing).
- v. Randomization procedures are described in [Section 4.4.1](#).
- w. Prior to dosing, all patients will receive premedications administered at least 60 minutes prior to the start of infusion of study drug. The regimen is described in [Section 5.3.1](#).
- x. The patient's infusion site should be assessed for signs of any localized reaction during the infusion and for 30 minutes after the end of the infusion. The patient will remain at the study site for 1 hour following completion of dosing for observation and completion of assessments.
- y. Patients who discontinue study drug due to rapid disease progression based on the 9-month efficacy assessments will continue on to the Modified Visit Schedule (See [Table 1-3](#)).
- z. Assessment must be completed at a single time point during one of the specified visits, at the discretion of the investigator.

Table 1-2: Schedule of Assessments; Week 39 to Week 86 (Follow-up) / Early Withdrawal

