1.2.7.2. Pharmacokinetic Parameters

Blood samples for determination of patisiran pharmacokinetics (PK) will be collected as outlined in the schedule of assessments. Plasma siRNA, DLin-MC3-DMA, and PEG₂₀₀₀-C-DMG concentrations will be determined in all patients in order to estimate individual PK parameters such as peak and trough concentrations.

Urine will be collected with void volume recorded for all patients at time points specified in the schedule of assessments to determine concentration of siRNA and 4-dimethylaminodibutyric acid (the metabolite of DLin-MC3-DMA) after dosing with study drug.

Pharmacokinetic parameters will be estimated by the Clinical Pharmacology and Pharmacometrics Department at Alnylam Pharmaceuticals.

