2. PATIENT POPULATION

2.1. Population Definitions

The following patient populations will be evaluated and used for presentation and analysis of the data:

- Modified Intent-to-Treat (mITT) population: All patients who were randomized and received at least 1 dose of patisiran or placebo. Patients will be analyzed according to the treatment to which they were randomized.
- Per-protocol (PP) population: All randomized patients who received at least 1 dose of patisiran or placebo, completed baseline and either 9-month or 18-month mNIS+7 and Norfolk QOL assessments, and did not experience any major protocol deviations that may impact the efficacy results (Section 2.2). Patients will be analyzed according to treatment received.
- Safety population: All patients who received at least 1 dose of patisiran or placebo. Patients will be analyzed according to the treatment received.
- PK population: All patients in the Safety Population who provided at least 1 PK concentration measurement.

The primary population for efficacy analysis will be the mITT population; the primary endpoint and the first secondary endpoint (Norfolk QOL) will also be analyzed using the PP population. The remaining secondary and exploratory efficacy endpoints will be analyzed using the mITT population only. Safety analysis will be conducted in the safety population. PK analysis will be conducted in the PK population.

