3.2. General Methods

All data listings that contain an evaluation date will contain a study day relative to the day of the first dose of study drug, which is designated as Day 1. On-treatment study days will be calculated as evaluation date – first dose date +1 and pre-treatment days will be calculated as evaluation date – first dose date. For example, the day prior to study drug administration will be Day -1, the first dose day of study drug will be Day 1 and the day after the first dose of study drug will be Day 2, etc.

All output will be incorporated into Microsoft Word files, sorted and labeled according to the International Conference on Harmonisation (ICH) recommendations, and formatted to the appropriate page size(s).

For categorical variables, summary tabulations of the number and percentage of patients within each category (with a category for missing data) of the parameter will be presented. For continuous variables, the number of patients, mean, median, standard deviation (SD), minimum, and maximum values will be presented.

Laboratory data (including vitamin A and RBP) collected and recorded as below the limit of detection will be set equal to the lower limit of detection for the calculation of summary statistics.

For assessments that are repeated multiple times on the study day (e.g., 10-meter walk tests, IENFD, SGNFD, etc.), the average will be calculated unless otherwise noted.

Formal statistical hypothesis testing will be performed on the primary and secondary efficacy endpoints with all tests conducted at the nominal 2-sided 0.05 level of significance. Secondary endpoints will be tested in a prespecified hierarchy (Section 3.6). Summary statistics will be presented, as well as 2-sided 95% confidence intervals on selected parameters, as described in the sections below.

All summaries will be presented by treatment arm. All data recorded on the CRF will be included in data listings.

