4.5.1.2. Plasma ALN-TTR02 Pharmacokinetic Parameters

Model independent PK parameters to be calculated by study visit include:

- Observed post-infusion peak concentration (C_{max})
- Observed 30 min post-infusion concentration (C_p (30 min))
- Observed pre-infusion trough concentration (C_{trough})

In addition, steady-state C_{max} (C_{max_ss}), steady-state C_{trough} (C_{trough_ss}) and steady-state C_p(30 min) (C_{p_ss}(30min)) will be calculated. C_{trough_ss} is the average C_{trough} on Days 253, 400 and 547. C_{p_ss}(30 min) is the average C_p(30 min) on Days 253 and 547. C_{max_ss} is the C_{max} on Day 400.

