4.5.2. Statistical Methods

Descriptive statistics for plasma PK parameters will include the number of patients, mean, SD, coefficient of variation (CV), median, minimum, maximum, geometric mean and geometric CV%.

The plasma C_{max}, C_p (30min) and C_{trough} of ALN-18328 (siRNA), DLin-MC3-DMA and PEG₂₀₀₀-C-DMG will be summarized by nominal sampling day. Urinary amounts of ALN-18328 and 4-dimethylaminobutyric acid recovered will be estimated as urine concentration

times the associated urine volume and will be summarized by nominal sampling day. Mean concentrations (+/- SD) will be plotted versus nominal sampling time.

Steady-state PK parameters for ALN-18328 (siRNA), DLin-MC3-DMA and PEG₂₀₀₀-C-DMG will be summarized overall and by subgroup (gender, anti-drug antibody status).

Plasma concentration data will be presented in by-patient listings.

The PK-PD relationship between the plasma concentration of ALN-18328 and the percent change from baseline in TTR protein, vitamin A and RBP will be explored graphically.

The PK exposure-response relationships for the primary endpoint (mNIS+7), TTR, and incidence of relevant AEs may also be explored. These may be summarized by ALN-18328, DLin-MC3-DMA and PEG₂₀₀₀-C-DMG PK exposure quartiles at 18-months (Day 546).

Population PK and exposure-response modeling will be reported separately.

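### The SAP sets below-quantification PK concentrations to zero, yet requires geometric means and geometric CVs and gives no rule for the zeros

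*SAP*

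**What the plan says.** SAP 4.5.1.1, which covers both plasma and urine concentrations, states: "Concentration values that are below the limit of quantification (LLOQ or BLQ) will be set to zero for analysis".

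SAP 4.5.1.2 defines the plasma parameters by visit. One is the "Observed pre-infusion trough concentration"; the others are the post-infusion peak and the 30-minute post-infusion value. Steady-state trough is the average of the troughs on Days 253, 400 and 547.

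SAP 4.5.2 lists the descriptive statistics for plasma PK parameters. They are the number of patients, mean, SD and CV, followed by "median, minimum, maximum, geometric mean and geometric CV"%. Parameters are summarised by nominal sampling day. Steady-state parameters are also summarised overall, by gender and by anti-drug antibody status.

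Three other places bear on how often zeros would arise.

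- Protocol Table 1-1, in the plasma PK footnote, schedules a Day 0 sample before the first infusion.
- SAP 1.2.7.2 says that plasma "concentrations will be determined in all patients in order to estimate individual PK parameters such as peak and trough concentrations".
- SAP 2.1 defines the "PK population: All patients in the Safety Population who provided at least 1 PK concentration measurement", which does not exclude placebo patients.

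For laboratory data, including vitamin A and RBP, SAP 3.2 uses a different convention: values below detection "will be set equal to the lower limit of detection for the calculation of summary statistics".

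**The concern.** Both geometric statistics are computed from logarithms, and the logarithm of zero does not exist. The two instructions therefore cannot both be followed wherever a value is below the limit of quantification (BLQ), and no section says which gives way. The zeros could be kept, excluded, replaced, or reported as not calculated. The choice would fall to whoever programs the table.

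The likely silent outcome is that zeros become missing values in the log step and drop out. The geometric statistics for trough would then describe only patients with measurable drug, and would show exposure as higher and less variable than it is. If the BLQ share differs between nominal days or groups, comparisons of geometric means would be distorted as well.

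**Working it through.** The plan states no figure on this point, so there is nothing to reproduce. The check has four steps.

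**1. What a zero does.** Geometric mean (GM) = exp(mean of ln x). Geometric CV = sqrt(exp(variance of ln x) − 1). Take the values 0, 1, 2, 4. The logs are −∞, 0, 0.693 and 1.386. The geometric mean is 0 and the variance of the logs, and hence the geometric CV, is undefined. With the zero dropped, the mean log is (0 + 0.693 + 1.386)/3 = 0.693 and the geometric mean is 2.

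**2. Where zeros can be expected.** The Day 0 pre-dose sample precedes any drug. If it is tabulated as a trough, it should be BLQ in essentially everyone. Later troughs are drawn about 21 days after the previous dose. Samples at the end of infusion or 30 minutes later should rarely be BLQ on active drug; that is a judgement, since no assay limit is given. Steady-state trough is zero only if every available trough is BLQ. With three troughs and BLQ share p at each, the chance is p³ if they are independent within a patient: 0.1%, 2.7% and 12.5% at p = 10%, 30% and 50%. It rises to p if the same patients are BLQ every time.

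**3. Bias if zeros are dropped.** Assumptions: concentrations are lognormal with true CV c, and a share p lies below the limit.

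- s = sqrt(ln(1 + c²)), z = Φ⁻¹(p), λ = φ(z)/(1 − p)
- GM ratio, reported to true = exp(sλ)
- Reported geometric CV = sqrt(exp(s²(1 + zλ − λ²)) − 1)

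Example with c = 100% and p = 30%: s = 0.8326, z = −0.5244 and λ = 0.4967. The GM ratio is exp(0.8326 × 0.4967) = 1.51. The log variance is 0.6931 × (1 − 0.2605 − 0.2467) = 0.3416, which gives a geometric CV of 64%.

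| True CV | BLQ share | GM ratio | Reported geometric CV |
|---|---|---|---|
| 30% | 10% | 1.06 | 25% |
| 30% | 30% | 1.16 | 21% |
| 30% | 50% | 1.26 | 18% |
| 100% | 10% | 1.18 | 80% |
| 100% | 30% | 1.51 | 64% |
| 100% | 50% | 1.94 | 54% |

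**4. Half the limit (LLOQ/2) as a substitute.** Each BLQ log value becomes sz − ln 2. The GM ratio is then exp(p(sz − ln 2) + sφ(z)). At c = 30% and p = 50% this is exp(−0.3466 + 0.2936 × 0.3989) = 0.795. For 10%, 30% and 50% BLQ the results are:

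- CV 30%: GM ratio 0.95, 0.86, 0.80; the geometric CV rises to 43%, 52%, 51%.
- CV 100%: GM ratio 0.97, 0.95, 0.99.

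Substitution therefore works well when variability is high. When variability is low, it understates the geometric mean by up to about 20% and overstates the geometric CV.

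**The case against.** The best case against raising this is that it is one missing sentence for descriptive tables. Seven of the nine statistics in SAP 4.5.2 accept zeros, a minimum or median of 0 would show BLQ values openly, and by-patient listings of plasma concentrations are required. Population PK and exposure-response modelling are reported separately. No hypothesis test depends on the geometric summaries. All of that stands, and it sets the size of the point.

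Five stronger readings are tempting, and the documents do not support them.

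- A reader might infer that dropping zeros inflates both geometric statistics. Only the geometric mean rises; losing the low tail shrinks the geometric CV.
- A reader might infer that the whole PK table would describe only patients with measurable drug. The arithmetic statistics and the listings keep the BLQ patients.
- A reader might extend the problem equally to the peak and 30-minute values. Those are post-infusion samples, where BLQ is not expected on active drug.
- A reader might conclude that the gender and antibody comparisons are seriously distorted. They use steady-state parameters, and averaging over three days makes a zero trough less likely, though not impossible.
- A reader might take placebo zeros to be mixed with active values. SAP 3.2 presents all summaries by treatment arm, so any placebo values would normally form a separate column. The wording on who enters the PK summaries is still loose.

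It is also fair to object that LLOQ/2 is only a convention. Step 4 of the working shows this, so the essential request is a stated rule and not that particular value.

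**Conclusion.** The point holds, at low severity. Read literally, the zero rule and the required geometric statistics give a geometric mean of 0 and an undefined geometric CV wherever a BLQ value occurs. This is a stated rule that yields an unusable statistic, so it is more than a missing detail. If zeros are dropped in programming, the geometric mean is overstated by 6% to 94% and the geometric CV is understated, over assumed BLQ shares of 10% to 50% and true CVs of 30% to 100%. That range rests on lognormal concentrations and on BLQ shares and CVs that the documents do not give. If few post-dose troughs are BLQ, the practical effect is small.

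The scope is mainly trough by nominal day, including the Day 0 pre-dose sample. Primary and secondary efficacy inference is unaffected.

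**What to change.** Amend SAP 4.5.1.1 and 4.5.2 as follows.

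1. Keep zero for BLQ values in arithmetic summaries and plots.
2. Exempt the geometric mean and geometric CV from the zero rule, and state one rule for BLQ values after the first dose. Two acceptable choices are LLOQ/2, labelled as a convention with the limits shown in step 4, or reporting these statistics as not calculated when any zero is present.
3. Report the number and percentage BLQ at each time point.
4. Suppress the geometric statistics when more than half the values are BLQ.
5. Limit geometric summaries to patisiran-treated patients and samples taken after the first dose.

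The cost is a few sentences of SAP text and one extra row in the PK tables; no new data are needed. If LLOQ/2 is chosen, one table will carry two BLQ conventions, so a footnote should say which statistics use which.

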4.5.1.2. Plasma ALN-TTR02 Pharmacokinetic Parameters

Model independent PK parameters to be calculated by study visit include:

- Observed post-infusion peak concentration (C_{max})
- Observed 30 min post-infusion concentration (C_p (30 min))
- Observed pre-infusion trough concentration (C_{trough})

In addition, steady-state C_{max} (C_{max_ss}), steady-state C_{trough} (C_{trough_ss}) and steady-state C_p(30 min) (C_{p_ss}(30min)) will be calculated. C_{trough_ss} is the average C_{trough} on Days 253, 400 and 547. C_{p_ss}(30 min) is the average C_p(30 min) on Days 253 and 547. C_{max_ss} is the C_{max} on Day 400.

4.5.2. Statistical Methods

Descriptive statistics for plasma PK parameters will include the number of patients, mean, SD, coefficient of variation (CV), median, minimum, maximum, geometric mean and geometric CV%.

The plasma C_{max}, C_p (30min) and C_{trough} of ALN-18328 (siRNA), DLin-MC3-DMA and PEG₂₀₀₀-C-DMG will be summarized by nominal sampling day. Urinary amounts of ALN-18328 and 4-dimethylaminobutyric acid recovered will be estimated as urine concentration

times the associated urine volume and will be summarized by nominal sampling day. Mean concentrations (+/- SD) will be plotted versus nominal sampling time.

Steady-state PK parameters for ALN-18328 (siRNA), DLin-MC3-DMA and PEG₂₀₀₀-C-DMG will be summarized overall and by subgroup (gender, anti-drug antibody status).

Plasma concentration data will be presented in by-patient listings.

The PK-PD relationship between the plasma concentration of ALN-18328 and the percent change from baseline in TTR protein, vitamin A and RBP will be explored graphically.

The PK exposure-response relationships for the primary endpoint (mNIS+7), TTR, and incidence of relevant AEs may also be explored. These may be summarized by ALN-18328, DLin-MC3-DMA and PEG₂₀₀₀-C-DMG PK exposure quartiles at 18-months (Day 546).

Population PK and exposure-response modeling will be reported separately.

4.6. Safety Analyses

Safety analyses will be conducted using the Safety population. All safety summaries will be descriptive and will be presented by treatment arm.

4.6.1. Study Drug Exposure

Duration of drug exposure will be defined as (the last dose of study drug – the first dose of study drug + 21)/30.44 months. Duration of drug exposure, the total number of doses received, duration of infusion (per infusion) and amount of study drug received (per infusion and in total) will be summarized by descriptive statistics. Summaries of the numbers and percentages of patients with missing dose, and the number of missing doses per patient will also be provided. The total amount of drug received and the total volume infused will also be summarized.

The number of patients who experienced interruptions of infusions for any reason will be tabulated, as well as the number of patients with infusion interruptions due to an acute infusion reaction.

Dosing information for each patient will be presented in a data listing.

4.6.2. Adverse Events

All AEs will be coded using the MedDRA coding system (version 18.0 or later) and displayed in tables and data listings using SOC and preferred term.

Analyses of AEs will be performed for those events that are considered treatment-emergent, where treatment-emergent is defined as any AE with onset during or after the administration of study drug through 28 days following the last dose of study drug. In addition, any event that was present at baseline but worsened in intensity or was subsequently considered drug-related by the Investigator through the end of the study will be considered treatment-emergent. Events with a fully or partially missing onset date will be assumed to be treatment emergent unless it can be unequivocally determined (from the partial onset date and/or a partial or complete stop date) that the event occurred prior to the first administration of study drug.

Adverse events will be summarized by the numbers and percentages of patients reporting a given AE. A patient contributes only once to the count for a given AE (overall, by SOC, by preferred term). Overall event counts and frequencies may also be summarized.

An overall summary of AEs will include the number and percentage of patients with any AE, any AE assessed by the Investigator as related to treatment (definite or possible relationship), any severe AE, any severe AE related to treatment, any serious AE (SAE), any SAE related to treatment, any AE leading to treatment discontinuation, any study drug related AE leading to treatment discontinuation, any AE leading to study withdrawal, any study drug related AE leading to study withdrawal, and any deaths.

Tabulations by SOC and preferred term will be produced for the following: all AEs; AEs related to treatment; severe AEs; AEs leading to infusion interruption; AEs leading to drug delay; AEs leading to treatment discontinuation; AEs leading to study withdrawal; and SAEs. Separate tables will be provided summarizing signs and symptoms of IRRs (overall and by premedication regimen) and AEs related to premedication (overall and by premedication regimen) by SOC and preferred term. The incidence and frequency of AEs and IRRs over time will also be summarized by SOC and preferred term. Adverse events and AEs related to treatment will also be tabulated by preferred term in decreasing order in frequency in the patisiran arm. Adverse events and SAEs will also be summarized by SOC and preferred term for the cardiac subpopulation.

Separate tables will present AE incidence rates by maximum relationship to study drug and by maximum severity. Patients who report multiple occurrences of the same AE (preferred term) will be classified according to the most related or most severe occurrence, respectively.

AEs mapping to the standardized MedDRA query (SMQ) Depression and Suicide/Self-injury will be summarized by preferred term. Adverse events mapping to the SMQ Drug Related Hepatic Disorder will be summarized by SOC and preferred term. Adverse events mapping to the SMQ Malignant or Unspecified Tumors will be summarized by high level term and preferred term. Other SMQs or AE groupings may be evaluated.

All AEs will be presented in patient data listings. Separate listings will be provided for death, SAEs, AEs leading to treatment discontinuation, AEs leading to study withdrawal, IRRs, AEs related to premedications, AEs related to study procedures, and AEs mapping to the SMQ as described above. A listing of patients who underwent liver transplant will also be provided.

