8.5 Adverse Event Reporting Period

AEs and SAEs will be reported according to the following timeframes:

- For patients who complete the study, AEs will be assessed through the End of Study visit on Day 567 or the Follow-up visit on Day 602 (depending whether or not the patient plans to roll over to the open-label extension study). All AEs that occur after the start of study drug administration on Day 0 must be reported in detail on the appropriate CRF page and followed to satisfactory resolution, or through the end of study visit on Day 567 or Day 602 (depending whether or not the patient plans to roll over to the open label extension study) after the last dose of study drug administration. SAEs will be followed through the end of study visit on Day 567 or Day 602 (depending whether or not the patient plans to roll over to the open label extension study), or until satisfactory resolution, or until the SAE is considered by the Investigator to be chronic or the patient is stable, whichever occurs first.
- For patients who meet the criteria for Rapid Disease Progression at Month 9 and receive their last dose of study drug on Day 252 but remain on the study, AEs will be followed through Day 294. Following Day 294, only study-procedure-related AEs will be collected (e.g., skin-biopsy-related AE, venipuncture-related AE). SAEs will be followed by the Investigator until satisfactory resolution or the Investigator deems the SAE to be chronic or stable.

- For patients who withdraw from the study early, ongoing AEs will be followed until resolution or 28 days from last dose, whichever occurs first. SAEs will be followed by the Investigator until satisfactory resolution or the Investigator deems the SAE to be chronic or stable.

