3. GENERAL STATISTICAL METHODS

3.1. Sample Size Justification

For the estimation of sample size, a mean (\pm SD) mNIS+7 progression rate (primary endpoint) in the placebo group of 24 ± 16 points over 18 months was estimated using natural history data [1] from FAP patients. A sample of 154 patients provides 90% power for a 2-sided t-test with an 8.95-point (37.5%) mean difference between treatment arms in the primary endpoint at 2-sided $\alpha = 0.05$. Assuming a 25% random premature discontinuation rate (due to liver transplantation or other factors), the required sample size for this study is approximately 200.

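### Adverse events are reported only as percentages of treated patients, although the counting window shortens with every discontinuation; rates per patient-year should stand beside them

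*SAP*

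**What the plan says.** SAP 4.6 analyses safety in all treated patients, descriptively and by arm. In 4.6.2, "Adverse events will be summarized by the numbers and percentages of patients reporting a given AE", and a patient counts once per event. Event counts are optional: "Overall event counts and frequencies may also be summarized". One time-related summary is firm: "The incidence and frequency of AEs and IRRs over time will also be summarized by SOC and preferred term". The section calls some tables incidence rates, but gives them no person-time denominator.

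The tables are limited to treatment-emergent events, meaning onset from first dose "through 28 days following the last dose of study drug". Events present at baseline that worsen, or that are later judged drug-related, are added through the end of the study.

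Protocol 8.5 sets separate collection limits. Rapid progressors who "receive their last dose of study drug on Day 252 but remain on the study, AEs will be followed through Day 294"; after that, collection is limited to procedure-related events ("Following Day 294, only study-procedure-related AEs will be collected"). Completers are dosed through Day 546 (Protocol 6.2.2), with collection to Day 567 or Day 602 depending on entry to the extension study.

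SAP 4.6.1 defines exposure ("Duration of drug exposure will be defined as" the first-to-last-dose interval plus 21 days, in months), but 4.6.2 does not use it. SAP 3.8.2 plans Kaplan-Meier time to treatment discontinuation by arm, and SAP 4.1 gives disposition with reasons by arm.

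**The concern.** A percentage of patients with an event depends on both the hazard and the length of observation. Here the length is tied to time on drug, so each discontinuation shortens the window while the patient stays whole in the denominator. If one arm stops earlier on average, its percentages fall for that reason alone.

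A difference between arms is plausible. Meeting the rapid-progression criterion at 9 months gives the patient an option to stop drug, and comparing that criterion between arms is an exploratory objective (Protocol 2.3). If the drug works, exits for worsening should fall more on placebo, and patisiran, observed for longer, would look worse tolerated than it is. If patisiran patients leave earlier, the distortion runs the other way. At stake is the reading of the main safety tables.

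**Working it through.** **Figures in the plan.** The adverse event section gives no number to reproduce; the one relevant planning figure is the 25% in SAP 3.1. With a difference of 8.95, SD 16, two-sided alpha 0.05, 90% power and 2:1 allocation, the normal formula gives 51 × 3 = 153, against the stated 154. Then 154 / 0.75 = 205.3, or 206, against about 200. So 25% is an overall rate in a 2:1 trial.

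**Windows.** Rapid progressors who stop: 252 + 28 = 280 days. Completers: 546 + 28 = 574 days (567 for extension entrants, a negligible change). 280 / 574 = 49%.

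**Rapid progression alone.** Protocol 1.4 expects fewer than 5% of patients, so at most 0.05 × 200 = 10. In the extreme case all are on placebo and all stop: 10 / 66.7 = 15% of that arm. The gap between arms is 0.15 × (risk at 574 days − risk at 280 days). For a 50% risk at 574 days and constant hazard, risk at 280 days is 1 − 0.5^(280/574) = 28.7%, so the gap is 0.15 × 21.3 = 3.2 points. Over all risks, the largest gap is about 3.9 points.

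**All discontinuation, illustrated.** Assumptions (mine): constant and equal hazard, stopping times uniform over 18 months, risk I = 30% over 18 months, observation ending at the last dose.

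- 18h = −ln(0.7) = 0.3567.
- Mean risk in a patient who stops: m = 1 − I/(18h) = 1 − 0.30/0.3567 = 0.1589.
- Crude percentage in an arm with discontinuation d: (1 − d) × 0.30 + d × 0.1589.
- Under 2:1, each pair satisfies (placebo + 2 × patisiran) / 3 = 25%.

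| Placebo / patisiran stopping | Mean months (18 − 9d) | Placebo % | Patisiran % | Ratio |
|---|---|---|---|---|
| 25 / 25 | 15.8 / 15.8 | 26.5 | 26.5 | 1.00 |
| 30 / 22.5 | 15.3 / 16.0 | 25.8 | 26.8 | 1.04 |
| 40 / 17.5 | 14.4 / 16.4 | 24.4 | 27.5 | 1.13 |
| 45 / 15 | 14.0 / 16.7 | 23.7 | 27.9 | 1.18 |

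**With the 28-day tail.** Set the 30% risk over 574 days, so h = 0.3567/574 per day. Then m = 1 − exp(−28h) × [1 − exp(−546h)]/(546h) = 0.1666. The ratio is 0.2767/0.2467 = 1.12 for 40/17.5 and 0.2800/0.2400 = 1.17 for 45/15; 30/22.5 stays at 1.04.

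**Per unit of time at risk.** For a window T, the expected number of first events is 1 − exp(−hT) and the expected time at risk, ending at the first event, is [1 − exp(−hT)]/h. Their ratio is h whatever the mix of windows. A 30% risk over 574 days gives 22.7 per 100 patient-years in both arms, a ratio of 1.00 in every row.

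**The case against.** Four stronger readings are tempting, and the documents do not support them.

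- A reader might infer that ending collection at Day 294 cuts events out of the tables. For this group the treatment-emergent window closes at about Day 280, so the 28-day rule binds first. At most, late worsening or reclassification as drug-related is lost.
- A reader might infer that the planned 25% makes the arms unequal. The text is "Assuming a 25% random premature discontinuation rate (due to liver transplantation or other factors"), with no split by arm. Taken as written, it gives a ratio of 1.00.
- A reader might infer that rapid progression drives a large distortion. Fewer than 5% are expected, and even the extreme case gives about 4 points.
- A reader might infer that the direction of any distortion would stay hidden. Exposure, Kaplan-Meier discontinuation and disposition, all by arm, would show which arm had less time on drug, and the over-time summary adds timing.

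Two further objections have force. Safety is descriptive, so no test or error rate is affected. And rates per patient-year presume a roughly constant hazard; for events concentrated early they can flatter the arm with longer exposure. What remains is that the planned summaries reveal an imbalance without adjusting for it, and nothing in the SAP commits to an adjusted comparison.

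**Conclusion.** The point holds as a gap in the safety reporting. The committed tables are crude percentages over a window that depends on time on drug, and no person-time rate is specified. Whether this distorts the comparison depends on differential discontinuation, which is plausible but not quantified in the documents. Under the assumed splits of an overall 25%, a 30% event with equal hazards shows ratios of 1.04 to 1.18, slightly less with the 28-day tail, and 1.00 if the arms stop equally. These sizes rest on a constant hazard, uniform stopping and assumed splits; they are not forecasts. Efficacy conclusions and the type I error rate are untouched.

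**What to change.** Keep every planned percentage. Before unblinding, add to SAP 4.6.2 the exposure-adjusted incidence of first events per 100 patient-years, by arm with 95% confidence intervals, for any adverse event, severe events, serious events, events leading to treatment discontinuation, death and the common preferred terms.

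Match numerator and denominator. Count only events with onset from first dose to the earlier of last dose plus 28 days and the end of adverse event collection, and use the same interval as time at risk, ending at the first event. Treatment-emergent events added later through the end of the study stay in the percentage tables but not in the rates. Report infusion-related reactions per infusion as well as per patient.

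The cost is a few extra columns from dates and dosing records already collected. For front-loaded events, a note should tell the reader to use the rates with the planned over-time summary.
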